11.3.4.4 Time to first 24-week CDA from baseline to EOS

The analysis for this variable follows the same approach as described in Section [11.3.3.2](#).

11.3.4.5 NEDA status at EOS

NEDA status at EOS is defined by the absence of confirmed relapses, Gd+ T1 lesions, new or enlarging T2 lesions, 12-week CDA, and an annual brain volume decrease of $\leq 0.4\%$ from baseline to EOS. If at least one of the five criteria is not fulfilled or the subject discontinues treatment prematurely, the subject is not considered to have achieved NEDA. NEDA will be analyzed using a logistic regression model with treatment as a factor and baseline EDSS category included in the model.

11.3.4.6 Change of MSFC Z-score and SDMT score from baseline to EOS by visit

The changes from baseline by visit up to the EOS assessment of both scores are analyzed using an ANOVA, similar to the analyses described in Section [11.3.4.2](#).

11.3.4.7 Change of FSIQ-RMS fatigue-related impacts from baseline to EOS by visit

The changes from baseline by visit up to the EOS assessment of fatigue-related impacts as measured by the impact sub-scales of the FSIQ-RMS will be analyzed similarly to fatigue-related symptoms in Section [11.3.3.4](#).

11.3.5 Analysis of the safety variables

The SAF will be used to perform all safety analyses.

If not otherwise stated, only treatment-emergent safety data (observations up to 30 days after study drug discontinuation) will be considered in tables and figures. All safety data will be included in listings, with flags for safety data not considered to be treatment-emergent.

Specific safety events (AEs, laboratory tests, ECG findings, etc.) will be considered. In general, they consist of one or more well-defined safety events which are similar in nature and for which there is a specific clinical interest in connection with ponesimod.

11.3.5.1 Adverse events

All AEs will be coded using the latest version of MedDRA available at the time of database closure.

11.3.5.1.1 Treatment-emergent AEs and SAEs

Treatment-emergent AEs and SAEs will be tabulated by study treatment, system organ class (SOC) and preferred terms within each SOC: the number and percentage of subjects who experienced at least one (S)AE, at least one (S)AE within each SOC and at least one S(AE) within each preferred term will be displayed. (S)AEs will also be summarized by decreasing frequency of preferred term. (S)AEs will also be tabulated by maximum intensity and relationship to ponesimod or placebo.

11.3.5.1.2 AEs of special interest and MACE

AEs of special interest and MACE will be summarized in the same way as stated in the previous section and compared between treatments using logistic regression. The definition of those AEs is provided in [Appendix 5](#).

AEs of special interest and MACE will also be summarized with point estimates and 95% CIs for event incidences adjusted for time on treatment and the relative risk ratio of ponesimod compared to placebo will be provided without adjustment for multiplicity.

In some cases, time to first onset of AEs of special interest or MACE will be displayed by Kaplan-Meier estimates. Subjects not experiencing the safety event will be censored at the minimum of the EOS date and 30 days after last dose of study drug. Where applicable, ponesimod will be compared to placebo using hazard ratios and corresponding 95% CIs from a Cox's regression model. For specific safety events where recurrence and/or duration are of interest, appropriate event history analysis such as an Andersen-Gill model for recurrent events will be described in the SAP.

11.3.5.1.3 AEs leading to premature discontinuation of study drug

(S)AEs leading to premature discontinuation of study drug will be summarized in a similar manner as that described in Section [11.3.5.1.1](#).

11.3.5.1.4 Post-treatment AEs and SAEs

Post-treatment (S)AEs occurring over 30 days after treatment discontinuation will be summarized in a similar manner as described in Section [11.3.5.1.1](#).

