3.5.3.2 Post-treatment observation period

Subjects who prematurely discontinue study drug and complete the 30-day safety follow-up including the FU visit, will enter the PTOP which lasts until 60 weeks after randomization of the last subject or until Week 156, whichever is first (i.e., planned EOT visit) irrespective of treatment completion. It consists of an abbreviated schedule of assessments at the time of the originally scheduled 12-weekly visits. The aim is to

follow-up with the subjects after discontinuation of study treatment and to collect long-term data while the subject possibly receives other approved MS therapies.

While participating in the PTOP, subjects may not be enrolled in another clinical trial. They may, however, withdraw their consent to participate to this study at any time [see Section 9.2].

3.5.3.3 *End-of-Study*

[figure not shown]
The study level EOS will occur after all subjects have completed the safety FU period or the last visit of the PTOP.

For an individual subject, EOS is reached when treatment, post-treatment safety FU, and if applicable, the PTOPs have been completed:

- For subjects who complete the treatment period, and for subjects who prematurely discontinue study treatment and do not enter the PTOP, the EOS visit corresponds to the 30-day FU visit (FU).
- For subjects who prematurely discontinue study treatment and enter the PTOP period, the EOS visit corresponds to the last visit of the PTOP.

The overall study design is shown in [Figure 1](#).

Figure 1 AC-058B302 study design

D = day; DMF = dimethyl fumarate; EOS = End-of-Study; EOT = End-of-Treatment; FU = follow-up; V = visit; W = week; *Lymphocyte tests every 4 weeks (\pm 3 days) until Week 24; ** Subjects participating in the lymphocyte subset sub-study will have an additional FU visit approximately 7 days after the last dose of study drug (FU7d).

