9 STUDY COMPLETION AND POST-STUDY TREATMENT/MEDICAL CARE

9.1 Study completion

For an individual subject, EOS is reached when treatment, safety FU period and, if applicable, the PTOP period have been completed:

- For subjects who remained under study treatment as defined per protocol (i.e., Week 156 or 60 weeks after randomization of the last subject [whichever occurs first]) and for subjects who prematurely discontinue study treatment and do not enter the PTOP, the EOS visit corresponds to Visit 20 (FU) 30 days after the last dose of study treatment.
- For subjects who prematurely discontinued study treatment (for whatever reason) and entered the PTOP, the EOS corresponds to the last PTOP visit performed.

The reason(s) for discontinuing the study along with who made the decision, if applicable (i.e., subject, investigator or Actelion) must be recorded in the eCRF.

EOS on a study level occurs at the time all subjects have completed their safety FU period and, if applicable, PTOP period as described above.

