10.1.5 Reporting of adverse events

All AEs occurring after study start (i.e., signing of informed consent) and up to 30 days after study treatment discontinuation or up to the last visit of the PTOP (i.e., Week 156 visit of the PTOP) (whichever is latest) must be recorded on specific AE pages of the eCRF. Actelion may contact the investigator to obtain further information.

Cardiac events

The first-dose administrator [see Section 3.7.4] must ensure that blinded study personnel at the study site, such as the treating neurologist, efficacy assessor, clinical coordinator / study nurse, and other personnel involved in the clinical care and management of the subject, do not have access to Day 1 and day of re-initiation of study drug post-dose BP assessments or ECGs interpretation reports, or to AEs with onset after the study drug intake on Day 1 or on the first day of re-initiation of study drug and which are resolved at the time of discharge.

However, significant findings (e.g., new ECG abnormalities, bradycardia) that meet the definition of an AE must be recorded on the AE page of the eCRF.

On Day 1 and on the first day of re-initiation of study drug when post-dose monitoring is required, significant findings that, in view of the first-dose administrator, meet the definition of an AE, have an onset after the study drug intake, and are resolved at the time of discharge of the subject from cardiac monitoring, must be reported directly on the AE page of the separate eCRF by the first-dose administrator / delegate. These AEs will not be visible to any of the blinded study personnel at the study site. All other significant findings on Day 1 and on the first day of re-initiation of study drug when post-dose monitoring is required but unresolved at the time of discharge from cardiac monitoring of the subject, which in her/his view meet the definition of an AE, must be reported to the principal investigator / treating neurologist who will record these events on the AE page of the eCRF. Similarly, any AEs with onset on Day 1 or on the first day of study drug re-initiation when post-dose monitoring is required leading to the premature discontinuation of study drug must be reported by the first-dose administrator to the principal investigator / treating neurologist who will record these events on the AE page of the eCRF.

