11.1.5 Safety set

The safety set (SAF) includes all subjects who received at least one dose of study treatment. Subjects will be analyzed based on actual treatment taken.

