11.1.7 Usage of the analysis sets

The FAS, ARS, and the PPS are used for the analysis of the primary and the secondary endpoints. Results for the primary and secondary efficacy endpoints based on the PPS and ARS will supplement those based on the FAS and assess the robustness of treatment effects.

Other MRI, clinical exploratory endpoints and other exploratory endpoints will be analyzed using the FAS.

All safety data will be analyzed using the SAF.

The usage of other analysis sets will be described in the SAP.

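### Adverse events more than 30 days after the last dose are to be shown as a percentage of all treated subjects, although almost only PTOP subjects are followed that long

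*Protocol*

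**What the plan says.** Three statements in the protocol together determine the table.

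- Section 11.3.5.1.4: "Post-treatment (S)AEs occurring over 30 days after treatment discontinuation will be summarized in a similar manner" as in Section 11.3.5.1.1. That section reports, by study treatment, system organ class and preferred term, "the number and percentage of subjects who experienced at least one (S)AE".
- Section 11.3.5: "The SAF will be used to perform all safety analyses". Section 11.1.7 repeats it: "All safety data will be analyzed using the SAF". Neither makes an exception for the post-treatment table.
- Section 11.1.5: "The safety set (SAF) includes all subjects who received at least one dose of study treatment".

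Other sections determine who is still observed in that window. Under Section 10.1.5, adverse events are recorded "up to 30 days after study treatment discontinuation or up to the last visit of the PTOP", whichever comes later. For completers, and for early discontinuers who do not enter the PTOP, Section 9.1 states that "the EOS visit corresponds to Visit 20 (FU) 30 days after the last dose of study treatment". Only early discontinuers who enter the PTOP are followed further. Section 3.5.3.2 runs that period to Week 156 or to 60 weeks after the last randomisation, whichever is first.

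**The concern.** The denominator takes in every treated subject, while the numerator can come, with small exceptions, only from those in the PTOP. A completer contributes a zero because nobody was recording, not because nothing happened. PTOP time also differs greatly between subjects, since it depends on when each one stopped, and no allowance for it is stated.

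Apart from the summary of deaths (Section 11.3.5.1.5), this is the only adverse event summary the protocol specifies for the period. The time-adjusted incidences in Section 11.3.5.1.2 use time on treatment, and the Kaplan-Meier displays there censor no later than 30 days after the last dose. Yet this is the period in which Section 5.2.6 lifts the list of forbidden therapies, and Section 9.4 warns of a possibly raised risk of opportunistic infection after two immunomodulators. A reader looking here for late infections or malignancies would see a percentage that is not a risk in any observed group. If PTOP entry differs by arm, the contrast could suggest a difference in risk that is not there, or hide one that is.

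**Working it through.** **Plan's own figure.** The protocol states no post-treatment event rate, discontinuation rate or PTOP-entry rate, so there is nothing to reproduce on this point. Entry shares below are assumptions, shown over a range.

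**Formula.** Let d be the share of an arm's SAF that enters the PTOP, and r the share of those with at least one recorded event after day 30. Ignoring the small exceptions taken up under the objection:

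- SAF percentage = d × r
- Factor by which it is lower than r = 1/d
- Ratio of SAF percentages, ponesimod (P) to placebo (C) = (d_P / d_C) × (r_P / r_C)

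**Size of the dilution**, with r = 30% for illustration and 300 subjects per arm (Section 11.5.1):

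| d | Subjects in PTOP per arm | SAF percentage shown | Factor 1/d |
|---|---|---|---|
| 10% | 30 | 3.0% | 10.0 |
| 20% | 60 | 6.0% | 5.0 |
| 30% | 90 | 9.0% | 3.3 |
| 40% | 120 | 12.0% | 2.5 |
| 50% | 150 | 15.0% | 2.0 |
| 60% | 180 | 18.0% | 1.7 |

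**Effect on the arm contrast:**

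| d_P / d_C | r_P / r_C | Ratio shown on the SAF |
|---|---|---|
| 20% / 20% | 1 | 1.0 |
| 30% / 20% | 1 | 1.5 |
| 15% / 30% | 1 | 0.5 |
| 20% / 20% | 2 | 2.0 |
| 15% / 30% | 2 | 1.0 |
| 30% / 15% | 2 | 4.0 |

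With equal entry the ratio passes through unchanged. With unequal entry it is multiplied by d_P / d_C, which can create a difference or cancel one. Because r depends on how long subjects are followed, unequal PTOP duration acts in the same way through r.

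**Is unequal entry plausible?** Under Section 3.5.2.1 a confirmed relapse opens the option to stop study treatment and enter the PTOP. The planning values in Section 11.5.1 are annualised rates of 0.50 and 0.325, dispersion k = 1.3 and mean follow-up of 1.9 years. As a check on using them, the variance of the log rate ratio is (1/0.95 + 1/0.6175 + 2 × 1.3)/300, which gives 90.1% power against the stated approximate 90%. The share with at least one confirmed relapse is 1 − (1 + kμ)^(−1/k):

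- Placebo: μ = 0.50 × 1.9 = 0.95, share = 46%
- Ponesimod: μ = 0.325 × 1.9 = 0.6175, share = 36%

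These are shares offered the option, not shares that stop. The safety stopping rules in Section 5.1.12 may push ponesimod the other way. Imbalance is therefore plausible, but neither its net direction nor its size follows from the protocol.

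**The case against.** The strongest reply is that Section 11.3.5.1.4 names no denominator. It borrows a layout, and Sections 11 and 11.1.6 leave displays and further analysis sets to the SAP, which could restrict the table to subjects still followed. Section 11 also bases categorical percentages on non-missing observations. This stands in part: the SAF denominator comes from reading the sections together. But the set for safety is stated twice without exception, and a subject with no recorded event is ordinarily counted as event-free, not missing. A PTOP denominator in the SAP would depart from the protocol text.

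Other points carry weight:

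- A SAF percentage is a legitimate count of treated subjects with a recorded late event. It becomes misleading when read as a risk.
- The table has no planned test or model. Event counts appear whatever the denominator, and events that are not treatment-emergent are flagged in listings.
- A PTOP-only percentage conditions on something that happens after randomisation. These subjects are selected by relapse, toxicity or choice and may be on other MS therapies, so it does not give a clean arm contrast either.
- It is slightly too absolute to say that late events can be recorded only in the PTOP. The follow-up visit may fall as late as day 37 (Section 8.3.1.2), and later SAEs judged related still go to drug safety (Section 10.2.4.2). Both exceptions are small.

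**Conclusion.** The point holds. Followed as written, the percentage combines PTOP entry with event risk, is lower than the risk among followed subjects by 1/d, and carries no adjustment for PTOP time.

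A reader might infer that the rates are several-fold too low as a matter of fact. The protocol does not support that, because d is not given. The factor is 3 or more only if at most one third of treated subjects enter the PTOP, and it is 2 at one half. A reader might also infer that the arm contrast mainly reflects discontinuation. That is not established either: with balanced entry and duration there is no distortion, and the ratio of 1.5 rests on an assumed 30% against 20%. The supportable statement is that the contrast can be confounded by differential PTOP entry and duration.

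The treatment-emergent safety analysis and the efficacy conclusions are unaffected. The change is worth making because this is the main summary of late events and the correction is cheap.

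**What to change.** In Section 11.3.5.1.4, state that:

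- percentages are based on treated subjects followed for adverse events beyond day 30 after the last dose;
- incidence per 100 subject-years is given by arm for those subjects, with time from day 31 after the last dose to EOS as the denominator;
- the number of subjects followed and their total subject-years are shown for each arm in the table header;
- event counts by arm are kept;
- a footnote says that the subset is selected after randomisation and may be on other MS therapies, so the arm contrast is descriptive only.

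Define being followed by the recording period in Section 10.1.5, in practice PTOP entry, and not by the date of the follow-up visit. Otherwise completers seen on days 31 to 37 would return to the percentage denominator with at most 7 days each.

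The cost is a few lines of text and a different denominator in one family of tables. The dates needed are already collected.

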11.3.5.1.5 Deaths

Fatal SAEs occurring any time after the start of treatment will be summarized in a similar manner as described in Section [11.3.5.1.1](#).

11.3.5.2 Cardiac safety

Descriptive summary statistics by visit and study treatment will be provided for observed treatment-emergent values and absolute changes from baseline in numeric 12-lead ECG values (HR, PR, QRS, QT, QTcB, and QTcF). Data will be summarized from pre-dose to the post-dose assessments at 1 h, 2 h, 3 h, and 4 h on Day 1 and also at the re-initiation of study drug.

Notable abnormalities for selected 12-lead ECG variables (HR, PR, QT and QTc) will be summarized for all data of the 3-hour post-dose assessments on Day 1, Week 12 and also at the re-initiation of study drug.

In addition treatment-emergent morphological ECG abnormalities will be summarized that were not present before first study drug intake (using data from the ECG provider).

Cardiac safety events will be summarized as categorical variables.

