5.1.12 Study-specific criteria for interruption / premature discontinuation of study treatment

5.1.12.1 *Cardiovascular*

Subjects **must** be permanently discontinued from study drug if:

- the following change in HR is observed at any time throughout the study, as documented by 12-lead ECG:
 - HR < 30 bpm, or
 - HR < 40 bpm is sustained for at least 1 hour and is associated with symptoms of bradycardia (e.g., syncope, dizziness, or vertigo), or
- QTcF > 500 ms is observed at any time throughout the study, as documented by 12-lead ECG, or
- the subject does not meet the criteria for discharge from cardiac monitoring on Day 1, or on the first day of re-initiation of study drug following drug interruptions after 12 hours post-dose monitoring, or
- the subject needs to receive systemic chronic treatment with β -blockers, diltiazem, verapamil, digoxin, or any other anti-arrhythmic or HR lowering therapy [non-exhaustive list of drugs provided in [Appendix 3](#)].

FU monitoring will have to be provided until the event resolves, the condition is stable, or the change is regarded as no longer clinically relevant.

Continuous ECG monitoring is recommended for subjects who meet study drug discontinuation criteria related to bradycardia or other arrhythmia. Subjects who are permanently discontinued should not be discharged from the monitored setting before vital signs return to near baseline values and until there is no persisting ECG abnormality (e.g., QT prolongation, AV-block second degree or higher) or ongoing AE requiring (continued) cardiac monitoring, or until medically indicated. Any clinically relevant

finding meeting the definition of an AE will be recorded accordingly in the respective eCRF.

In case of any signs and symptoms of bradycardia or other arrhythmia (e.g., syncope, palpitations, etc.), at any time during the study treatment, the first-dose administrator and/or a cardiologist may be consulted. In case a cardiac origin is suspected, permanent discontinuation of study drug should be considered.

In case subjects experience sustained *de novo* or worsening of pre-existing hypertension during the course of the treatment with the study drug which, in the opinion of the investigator, cannot be adequately controlled by medications, study drug should be permanently discontinued.

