6.2 Safety endpoints

The treatment-emergent period is defined as the time from first study drug intake up to 30 days (inclusive) after last study drug intake. The following safety endpoints will be analyzed:

- Treatment-emergent AEs, SAEs, AEs of special interest[#], MACE, and AEs leading to premature discontinuation of study treatment;
- Treatment-emergent morphological ECG abnormalities (as defined by the ECG provider);
- Change in 12-lead ECG variables (HR, PR, QRS, QT, QT corrected for HR on the basis of Bazett's formula [QTcB], Fridericia's formula [QTcF]) from pre-dose to selected post-dose assessments (1 h, 2 h, 3 h, 4 h) on Day 1 and on day of re-initiation of study treatment when post-dose monitoring is required;
- Notable abnormalities* for selected 12-lead ECG variables (HR, PR, QT, QTc) at 3-hour post-dose assessment on Day 1, Week 12 and at the re-initiation of study treatment when post-dose monitoring is required;
- Treatment-emergent decrease of FEV₁ or FVC $> 20\%$ from baseline values or decrease of percent predicted FEV₁ or FVC > 20 percentage points from baseline values;
- Change in FEV₁ or FVC from baseline, absolute and % of absolute change to all timepoints up to EOS;

- Change from baseline to EOS versus change from baseline to EOT in FEV₁ or FVC (absolute and % of predicted);
- Among subjects with a decrease of > 200 mL or > 12% in FEV₁ or FVC from baseline to EOT, reversibility defined as a decrease of < 200 mL or < 12% in FEV₁ or FVC from baseline to last available post EOT follow-up;
- Treatment-emergent notable blood pressure abnormalities*;
- Treatment-emergent notable laboratory abnormalities*;
- Change in body weight from baseline to EOS;
- Treatment-emergent electronic self-rated version of the Columbia-Suicide Severity Rating Scale (eC-SSRS) suicidal ideation score of 4 or above, or a “yes” response on the eC-SSRS suicidal behavior item;
- Change in JCV serology from baseline up to EOS.

[#] The selection of AEs of special interest is based on the anticipated risks of treatment with ponesimod and on the events that may be related to MS co-morbidities (e.g., seizures or stroke) as described in [Appendix 5](#); the final list of AEs of special interest will be defined in the Statistical Analysis Plan (SAP).

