7.3 Safety assessments

The definitions, reporting and FU of AEs, SAEs and potential pregnancies are described in Section [10](#).

7.3.1 12-lead electrocardiogram

A standard 12-lead ECG will be recorded at all scheduled study visits with the subject in a fully rested supine position after the subject has been allowed to rest for a minimum of 5 minutes. Pre-dose ECG may also be performed at unscheduled visits (U1, U2, etc.).

Digital 12-lead ECG devices will be provided to each site by the central ECG laboratory for the duration of the study. Digital ECG recording must be performed for all subjects according to the study protocol schedule. The data records will be sent to the central ECG laboratory for central reading. The reports from the central ECG laboratory will be sent to the site within a few days. In addition, at all sites where the first-dose administrator is not adequately experienced in interpreting ECGs, at Visit 3 (Day 1) and on the day of re-initiation of study drug when post-dose monitoring is required, the pre-dose and post-dose ECGs required for evaluation of discharge criteria will be transmitted to the central ECG laboratory for expedited evaluation, and the ECG report will be returned to the site within approximately 1–2 hours from transmittal.

Details will be provided in the ECG laboratory manual.

At Visit 3 (Day 1) and visits for re-initiation of study drug when post-dose monitoring is required, the 12-lead ECG monitoring will be performed under the responsibility of the first-dose administrator. At all other visits it will be performed under the responsibility of the treating neurologist or the first-dose administrator, depending on the site setting [see Sections 3.7.2 and 3.7.4]. The first-dose administrator will ensure that blinded study personnel at the study site, such as the treating and evaluating neurologists, clinical coordinator / study nurse, and other personnel involved in the clinical care and management of study subjects, do not have access to post-dose ECGs at Visit 3 (Day 1) and at visits for re-initiation of study drug when post-dose monitoring is required (Visits I1, I2, etc.; see Section 8.4.2).

The following variables will be evaluated: HR (bpm), PR (ms), QRS (ms), QT (ms), QTc (ms), and any ECG findings. QTc (ms) will be calculated according to Bazett's and Fridericia's formula ($QTcB = QT/(RR)^{1/2}$ and $QTcF = QT/(RR)^{1/3}$, respectively).

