At Visit 3 (Day 1), the pre-dose ECG must be performed prior to randomization and the applicable point from exclusion criterion #12 (e.g., $HR < 50$ bpm, presence of second-degree AV block or third degree AV block, or a QTcF interval > 470 ms [females], > 450 ms [males]; see Section 4.4) must be ruled out. The first-dose administrator must provide the ECG results and interpretation to the principal investigator / treating neurologist and support her/him, if requested, to make a final decision on the subject's eligibility according to the inclusion/exclusion criteria.

During the treatment period ECGs must be performed at pre-dose. Additionally, at Visit 6 (Week 12), an ECG must also be performed at 3 hours post-dose. In case concomitant treatment with a QT-prolonging drug with known risk of Torsades de Pointes is needed, additional ECGs will be performed according to the guidance provided in Appendix 4.

At Visit 3 (Day 1) and on the day of re-initiation of study drug when post-dose monitoring is required [see Section 5.1.9], ECGs must be performed at pre-dose, and hourly (± 15 minutes) thereafter for a minimum of 4 hours and up to 12 hours post-dose. Subjects may be discharged from the cardiac monitoring if they meet the discharge criteria before 12 hours post-dose but no sooner than the (report of) ECG at 4 hours post-dose has been evaluated by the first-dose administrator [see Section 5.1.10]. If the subject does not meet the defined discharge criteria at 12 hours post-dose, the subject will be permanently discontinued from the study drug but will continue to be monitored, and additional ECG measurements will be performed until changes in ECG variables are no longer clinically relevant (i.e., discharge criteria are met; see Section 5.1.10), or until medically indicated.

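### The notable-ECG-abnormality endpoint counts only 3-hour post-dose ECGs, so no stated output gives the proportion of subjects per arm with an HR, PR or QTc outlier on any treatment-emergent ECG

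*Protocol*

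**What the plan says.** The endpoint in section 6.2 covers notable abnormalities of HR, PR, QT and QTc at the "3-hour post-dose assessment on Day 1, Week 12 and at the re-initiation of study" treatment when post-dose monitoring is required. The synopsis repeats this. The analysis text in 11.3.5.2 agrees: "Notable abnormalities for selected 12-lead ECG variables (HR, PR, QT and QTc) will be summarized for all data of the 3-hour post-dose assessments". It names the same three occasions.

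The trial collects many more ECGs than these:

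- Section 7.3.1: "A standard 12-lead ECG will be recorded at all scheduled study visits".
- For treatment visits: "During the treatment period ECGs must be performed at pre-dose", with a 3-hour post-dose ECG added at Week 12 only.
- On Day 1 and on monitored re-initiation days: "ECGs must be performed at pre-dose, and hourly" (within 15 minutes) "thereafter for a minimum of 4 hours and up to 12 hours post-dose".

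The permanent-discontinuation criteria in 5.1.12.1 use any ECG. One of them is "QTcF > 500 ms is observed at any time throughout the study, as documented by 12-lead ECG". The HR criteria (below 30 bpm, or below 40 bpm for at least 1 hour with symptoms) also apply at any time.

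The corresponding blood pressure and laboratory endpoints in 6.2 are treatment-emergent, with no time-point restriction.

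**The concern.** Section 1.3.2.4 describes transient change in heart rate and AV conduction as the most prominent safety signal with ponesimod, and section 1.4 says that the combination with DMF had not yet been tested in humans. A reader will therefore look for one figure per arm: the share of subjects who had a notable HR, PR or QTc value at some point on treatment. The one categorical endpoint for these variables cannot supply it, because it looks at a single hour on a few days.

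Three groups of ECGs fall outside it.

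- **Hours 1, 2 and 4 on Day 1 and at re-initiation.** A notable value there, but not at 3 hours, is not counted.
- **Hours 5–12.** Under section 5.1.10 these are required only for subjects who did not meet the discharge criteria at 4 hours. They enter neither this endpoint nor the numeric change endpoint, which stops at 4 hours.
- **Pre-dose visit ECGs and unscheduled ECGs.** Day 1 and re-initiation start at the 2 mg step (Table 4), so the Week 12 3-hour ECG is the only one in the endpoint recorded on the 20 mg maintenance dose. A subject who stops before Week 12, for instance after a Week 4 ECG, adds no maintenance-dose observation.

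An ECG value can thus lead to mandatory discontinuation without appearing in the table of notable ECG values.

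**Working it through.** The plan states no figure to reproduce. The check is a count of scheduled ECGs after the first dose, set against those the endpoint admits.

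**Inputs.** Visit schedule from sections 7.3.1 and 8.2.1 to 8.3.1.2; treatment-emergent window from 6.2 (up to 30 days inclusive after the last dose); admitted time points from 6.2 and 11.3.5.2. Assumed: all visits attended, discharge at 4 hours on Day 1, no re-initiation and no unscheduled ECG.

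**Subject treated to Week 156**

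| Occasion | ECGs | Admitted |
|---|---|---|
| Day 1, hours 1, 2, 3, 4 | 4 | 1 |
| Weeks 2 and 4, pre-dose | 2 | 0 |
| Week 12, pre-dose and 3 h | 2 | 1 |
| Weeks 24 to 144 every 12 weeks, pre-dose | 11 | 0 |
| EOT | 1 | 0 |
| **Total to EOT** | **20** | **2** |
| FU | 1 | 0 |
| **Total with FU** | **21** | **2** |

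The follow-up visit takes place 30 to 37 days after the last dose (8.3.1.2), so its ECG is treatment-emergent only if it falls on day 30. The share admitted is 2/20 = 10.0%, or 2/21 = 9.5% with FU.

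**Subject with EOT at Week 60.** Only Weeks 24, 36 and 48 remain from the fourth row: 4 + 2 + 2 + 3 + 1 = 12 to EOT, 13 with FU. The share admitted is 2/12 = 16.7%, or 2/13 = 15.4%.

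**What the other stated outputs give**

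| Output | Gives the proportion with any HR, PR or QTc outlier? |
|---|---|
| Numeric ECG values by visit, and at 1–4 h on Day 1 and re-initiation (11.3.5.2), with minimum and maximum (section 11) | No: extremes per time point, not subjects |
| Treatment-emergent morphological abnormalities (11.3.5.2) | No: a separate endpoint, not interval or rate cut-offs |
| Cardiac safety events as categorical variables (11.3.5.2) | Not stated: the protocol does not define them |
| Heart rate and rhythm AEs of special interest (11.3.5.1.2, Appendix 5) | No: reported as AEs |
| AEs leading to discontinuation (11.3.5.1.3) | No: only those who stopped |
| Listings of all safety data (11.3.5) | No: not summarised |

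The number of subjects missed cannot be computed from the protocol. The ECG cut-offs are left to the SAP, and no variability of HR, PR or QTc between hourly readings is given.

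**The case against.** **Other outputs carry the information.** This is largely right. Minimum and maximum by time point show extreme values by arm, a second-degree or higher AV block would be expected among the morphological findings, and everything is listed. A reader might infer that values forcing discontinuation go unreported. The documents do not support that: AEs leading to discontinuation are tabulated, Day 1 and re-initiation AEs that lead to discontinuation must be passed on for the AE page (3.7.4, 10.1.5), and the reason for stopping is recorded in the eCRF (5.1.11). Nor would different counts in the outlier and discontinuation tables be a contradiction, because their scopes differ.

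**The SAP can settle it.** Sections 6.2 and Appendix 6 leave the list of abnormalities and the abnormal values to the SAP, and Appendix 6 names HR, PR and QT/QTc without a time restriction. An SAP could add an any-time table without contradicting the protocol. But the time points of this endpoint are fixed in the protocol itself, in three places. Section 11.3.5 makes treatment-emergent data the default only where nothing else is stated, and here something else is.

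**A fixed time point is defensible.** The 3-hour ECG coincides with the 3-hour PK sample on Day 1 and at Week 12, and each subject has the same chance of being counted at those visits. An any-ECG count gives unequal opportunity, since hours 5–12, unscheduled ECGs and treatment duration all vary. This stands, and is the reason to keep the 3-hour table rather than replace it.

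**The share of ECGs overstates the loss.** Also fair. In the Week 156 case, 14 of the 20 are pre-dose ECGs at Weeks 2, 4, 12 and 24 to 144, and section 1.3.2.4 says that the HR and AV effects diminish with repeated dosing. The 10% is a share of recordings, not of information or of events.

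**Conclusion.** The point holds as a gap in one categorical safety endpoint. All three places that define it restrict it to the 3-hour ECG, while the blood pressure and laboratory endpoints have no such limit and the discontinuation criteria use any ECG. For a Week 156 completer, 2 of about 20 scheduled treatment-emergent ECGs can contribute; with EOT at Week 60, 2 of about 12. Both counts assume full attendance, discharge at 4 hours and no re-initiation or unscheduled ECG.

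What is missing is a stated proportion per arm with at least one HR, PR or QTc outlier on any treatment-emergent ECG. It does not follow that the trial loses these data or hides discontinuations, and how far the 3-hour table would understate the any-time rate is unknown from the protocol alone. No efficacy inference, sample size or stopping rule is affected. This is a moderate and inexpensive reporting improvement.

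**What to change.** In the synopsis, section 6.2 and section 11.3.5.2, add the number and proportion of subjects per arm with at least one notable HR, PR, QT or QTc abnormality on any treatment-emergent ECG. State that this covers all hourly post-dose ECGs on Day 1 and re-initiation days, including hours 5–12, and all scheduled and unscheduled visits within the treatment-emergent window. Keep the 3-hour summary as the by-timepoint display with equal ascertainment. The SAP supplies the cut-offs, as already planned.

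The cost is wording in three places and one extra table, from data already collected. Counts will be higher in both arms because more ECGs are searched, and subjects will differ in how many ECGs they contribute. The randomized placebo arm is the reference for reading them, and the table should say that the number of ECGs per subject varies.
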